5.4.1.2.15 Weight Loss

Anorexia and weight loss should be managed according to local standard of care including nutritional support. Pharmacologic therapy should be considered for appetite enhancement when not prohibited by a particular protocol.

5.4.1.2.16 Corrected QT Prolongation

The effect of orally administered cabozantinib 140 mg qd on QTc interval was evaluated in a placebo-controlled study in subjects with MTC. A mean increase in QTcF of 10-15 ms was observed after 4 weeks after initiating cabozantinib treatment. A concentration-QTc relationship could not be definitively established. Changes in cardiac wave form morphology or new rhythms were not observed. No cabozantinib-treated subjects in this study had a QTcF > 500 ms. Review of the larger safety database (including post marketing data) confirmed the absence of safety concerns associated with QT prolongation. There were no events of torsades de pointes reported.

Unless otherwise specified, only subjects with a baseline QTcF ≤ 500 msec are eligible for cabozantinib research studies. Cabozantinib should be used with caution in subjects with QT prolongation risk, a history of QT interval prolongation, or who are taking antiarrhythmics or drugs known to prolong the QT interval. Concomitant treatment with strong CYP3A4 inhibitors, which may increase cabozantinib plasma concentrations, should be avoided.

If at any time on study there is an increase in QTcF to an absolute value > 500 ms or an increase of > 60 ms above baseline, two additional ECGs must be performed with intervals not less than 3 min apart within 30 min after the initial ECG.

If the average QTcF from the three ECGs is > 500 ms or increased by > 60 ms above baseline, the following actions must be taken:

- Interrupt cabozantinib treatment.
- Hospitalize symptomatic subjects (e.g., with palpitations, dizziness, syncope, orthostatic
 hypotension, a significant ventricular arrhythmia on ECG) for a thorough cardiology evaluation
 and management.
- Consider cardiology consultation for asymptomatic subjects for evaluation and management
- Check electrolytes, especially magnesium, potassium and calcium; correct abnormalities as clinically indicated.
- Check concomitant medications for any medication that may have contributed to QT prolongation, and if possible, discontinue these medications (http://www.qtdrugs.org).

Repeat ECG triplicates hourly until the average QTcF is ≤ 500 ms and the average increase is ≤ 60 ms above baseline, or otherwise determined by consultation with a cardiologist or appropriate expert.

Subjects with QTc prolongation and symptoms must be monitored closely until the QTc elevation and symptoms have resolved. Cabozantinib treatment may be restarted at a reduced dose level if all of the following conditions are met:

- Symptoms are determined to be unrelated to the QT interval prolongation.
- Cabozantinib treatment has been interrupted through a minimum of 1 week following the return of the QTcF to ≤ 500 ms or return to ≤ 60 ms above baseline.
- QT prolongation can be unequivocally associated with an event other than cabozantinib administration and is treatable/has been resolved.
- Principal Investigator has reviewed all available information and has agreed to the continuation of study treatment

Following reinitiation of study treatment, ECGs must be repeated weekly for 2 weeks, then every 2 weeks for 1 month, then according to the protocol-defined time points.

Cabozantinib treatment must be permanently discontinued if either of the following applies:

- Cardiac evaluation confirms that symptoms are the consequence of QT interval prolongation.
- Recurrence of QTcF prolongation after reinitiation of study treatment at a reduced dose.

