Cabozantinib will be discontinued if a dose of 20-mg cabozantinib every other day (minimum dose) is not tolerated			

Dose Modifications of Cabozantinib for Treatment-Related AEs

Event	Management	
Grade 1 AEs	Add supportive care as indicated. Continue cabozantinib treatment at the current	
	dose level if AE is manageable and tolerable.	
Grade 2 AEs which are	Continue cabozantinib treatment at the current dose level with supportive care.	
tolerable and are easily		
managed		
Grade 2 AEs which are	At the discretion of the Investigator, cabozantinib should be dose reduced or	
intolerable and cannot be	interrupted.	
adequately managed		
	Note: It is recommended that dose holds be as brief as possible.	
Grade 3 AEs (except clinically	Cabozantinib should be interrupted unless the toxicity can be easily managed with a	
non-relevant laboratory	dose reduction and optimal medical care.	
abnormalities)		
	Note: It is recommended that dose holds be as brief as possible.	
Grade 4 AEs (except clinically	Subjects should have cabozantinib interrupted immediately.	
non-relevant laboratory	Discontinue cabozantinib unless the following criteria are met:	
abnormalities)	Subject is deriving clear clinical benefit as determined by the Investigator, and	
	approved by the Principal Investigator.	
	 Toxicity can be managed with a dose reduction following recovery to Grade 1 	
	(or baseline) and optimal medical care .	
Note: The dose delay and modi	fication criteria for specific medical conditions are provided in Section 5.4.1.2.	

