5.4.1.1 Cabozantinib Dose Reinstitution and Reescalation

If the subject recovers from his or her toxicities to CTCAE v.5.0 Grade \leq 1 or to the baseline value (or lower) and the toxicity was unrelated to cabozantinib, then cabozantinib may be restarted with no change in dose.

If the subject recovers from his or her toxicities to Grade \leq 1 or to the baseline value (or lower) the toxicity was deemed possibly related to cabozantinib, then cabozantinib may be restarted at a reduced dose.

Subjects who initiated treatment with cabozantinib at 40 mg and experience a possibly related AE of Grade 1 or 2 severity may be restarted with no dose change after recovery of the toxicities to \leq Grade 1 or to the baseline value (or lower) if appropriate supportive care can prevent or minimize the risk of the AE.

Subjects receiving a dose of 20 mg qod may be restarted at the same dose if deemed safe at the discretion of the investigator. Subjects unable to tolerate a dose of 20 mg qod should discontinue cabozantinib.

Re-escalation to the previous dose, (but not higher than 40 mg/day) may be allowed at the discretion of the Investigator for AEs which have resolved or recovered to Grade 1 (or baseline value) and deemed tolerable and easily managed by optimized supportive treatment. A minimum two-week interval is needed between resuming study treatment and the escalation to the next higher dose level. Dose re-escalation is not allowed for a drug-related dose reduction triggered by Grade 4 hematologic toxicities or by Grade 4 AEs affecting major organs (e.g., central nervous system, cardiac, hepatic, renal).

5.4.1.2 Guidelines for Management of Potential Adverse Events Associated with Cabozantinib Treatment

Subjects will be monitored for AEs from the time of 1st treatment through their last follow-up visit (100 days after the date of the last dose of study treatment.) Subjects will be instructed to notify their physician immediately at the onset of any AE. Seriousness, severity grade, and relationship to study treatment of AEs will be determined by the Investigator. AE severity will be graded by the Investigator in accordance with CTCAE v.5.0.

CONFIDENTIAL - Cabozantinib + Nivolimab + Ipililumab Protocol Required Elements

Management of severe or intolerable adverse reactions may require temporary dose reduction and/or interruption for cabozantinib.

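### The QTcF condition for restarting cabozantinib joins its two limits with *or*, so a subject who crossed both can meet it while still at a value that requires interruption

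*Combined protocol and SAP*

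**What the plan says.** Section 5.4.1.2.16 (Corrected QT Prolongation) applies the same two limits, 500 ms absolute and 60 ms above baseline, in three places.

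- **Interruption.** After a triplicate confirmation, action is mandatory as follows: "If the average QTcF from the three ECGs is > 500 ms or increased by > 60 ms above baseline". The first action listed is to interrupt cabozantinib.
- **End of intensive monitoring.** "Repeat ECG triplicates hourly until the average QTcF is ≤ 500 ms and the average increase is ≤ 60 ms above baseline", unless a cardiologist or other suitable expert decides otherwise.
- **Restart.** "Cabozantinib treatment may be restarted at a reduced dose level if all of the following conditions are met". One of the four conditions is at least one week off drug "following the return of the QTcF to ≤ 500 ms or return to ≤ 60 ms above baseline".

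The other three restart conditions are that any symptoms are judged unrelated to the QT prolongation, that the Principal Investigator has reviewed the case and agreed, and this one on cause: "QT prolongation can be unequivocally associated with an event other than cabozantinib administration and is treatable/has been resolved".

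Two other places bear on the point. Section 5.4.1.1 gives a general rule for resuming cabozantinib after recovery to Grade 1 or lower, or to baseline. The note under the dose-modification table in Section 5.4.1 says that "criteria for specific medical conditions are provided in Section 5.4.1.2".

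**The concern.** Interruption is triggered by either limit, so recovery should require both limits to be cleared. The rule for ending hourly ECGs does this. The restart rule does not, because clearing either limit is enough.

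The subject at issue is one whose QTcF crossed both limits. Read as written, the restart clock starts when the first limit is cleared, although the second is still exceeded and the interruption rule is still met. The section then gives two definitions of QTcF recovery, and the weaker one governs re-exposure.

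The ambiguity can cut both ways. A subject restarted in the overlap whose QTcF has not changed would meet the interruption rule again at the first weekly ECG after restart. A site could record that as a recurrence after restart, which the same section makes a ground for permanent discontinuation. So the wording risks early re-exposure in a cardiac-safety event, and it also risks avoidable loss of treatment.

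**Working it through.** The plan states no figure to reproduce here. The check is on logic and uses only the section's own limits.

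**Inputs.** Q is the mean QTcF and B the baseline, both in ms. The limits 500 and 60 come from Section 5.4.1.2.16. Baseline QTc up to 480 ms is allowed by Section 3.1, item 7b. The individual baselines below are assumptions chosen to show the range, and baseline QTc is taken as QTcF.

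**The three rules as formulas**

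- Interrupt: Q > 500 or Q − B > 60, which is Q > min(500, B + 60).
- End hourly ECGs: Q ≤ 500 and Q − B ≤ 60, which is Q ≤ min(500, B + 60).
- Start the one-week restart clock: Q ≤ 500 or Q − B ≤ 60, which is Q ≤ max(500, B + 60).

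The second rule is the exact complement of the first. The third is not. It overlaps the interruption rule wherever min(500, B + 60) < Q ≤ max(500, B + 60), a band of width |500 − (B + 60)| = |440 − B| ms.

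**Values that meet both the interruption rule and the restart condition (whole ms)**

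| Assumed baseline | B + 60 | Overlap | Width |
|---|---|---|---|
| 400 | 460 | 461–500 | 40 |
| 420 | 480 | 481–500 | 20 |
| 440 | 500 | none | 0 |
| 460 | 520 | 501–520 | 20 |
| 470 | 530 | 501–530 | 30 |
| 480 | 540 | 501–540 | 40 |

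Below a baseline of 440 ms, the subject in the overlap is under 500 ms but still more than 60 ms above baseline. Above 440 ms, the subject is within 60 ms of baseline but still over 500 ms.

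**Two courses in which both limits were crossed first**

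- Baseline 420: peak 510 (510 − 420 = +90), now 490 (+70). Since 70 > 60, interruption is still required and the hourly-ECG rule is not satisfied. Since 490 ≤ 500, the restart clock has started.
- Baseline 470: peak 545 (+75), now 520 (+50). Since 520 > 500, interruption is still required and the hourly-ECG rule is not satisfied. Since 50 ≤ 60, the restart clock has started.

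**With *and* in the restart condition**, the clock starts only at Q ≤ min(500, B + 60): 460 ms at baseline 400, 480 at 420, and 500 at 440, 460, 470 and 480. Enumeration in whole ms over baselines 380 to 480 found no value that met both this condition and the interruption rule.

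**The case against.** The best defence is that other parts of the protocol would stop an early restart.

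1. *Hourly triplicates continue until both limits are cleared.* A subject with one limit still exceeded would need about 168 consecutive hourly triplicates (7 × 24), or an expert's decision to stop them, to complete the week. The first is implausible. The second puts an expert in the loop, but that decision concerns ECG frequency and not restart. Once it is made, the restart condition is the only QTcF threshold specific to resuming drug, and no ECG immediately before restart is listed as a condition.
2. *Interruption is mandatory at any time, whereas restart is only permitted.* A careful investigator would keep holding the drug. That is a sensible way to settle the conflict, but it leaves the conflict in the text.
3. *All four restart conditions are required.* They are real safeguards, and QTcF alone does not permit restart. None of the other three sets a QTcF value, however, and the condition on cause can be read as met by a cause that is treatable but not yet resolved.
4. *Section 5.4.1.1 requires recovery to Grade 1 or baseline.* This is a partial safeguard. It does not clearly apply, because for an unrelated event it says "the toxicity was unrelated to cabozantinib, then cabozantinib may be restarted with no change in dose", while the QT section requires a reduced dose even though it demands a cause other than cabozantinib. The table note in Section 5.4.1 also sends specific conditions to Section 5.4.1.2.
5. *The* or *means return below whichever limit was crossed.* That is a fair reading for a subject who crossed one limit, and the point does not rest on that subject. It gives no answer for a subject who crossed both.

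The argument that the event is rare also stands. In the placebo-controlled study at 140 mg daily that the section describes, the mean QTcF increase was 10–15 ms, and "No cabozantinib-treated subjects in this study had a QTcF > 500 ms".

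**Conclusion.** The concern holds. For any baseline other than 440 ms, a subject who crossed both limits can meet the stated QTcF restart condition at a value where the same section requires cabozantinib to be held. The size of the overlap depends on assumed baselines. The result does not mean that cabozantinib can be restarted on QTcF alone.

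The documents give no frequency for this regimen. It is probably low, with 40 mg daily and 25 subjects planned, but that is a judgement from a different study and dose. This is an error in a safety rule and has no bearing on PFS, response, sample size or any analysis. It should be fixed because the rule concerns cardiac safety and the correction is very small.

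**What to change.** In the second restart condition of Section 5.4.1.2.16, replace *or* with *and*, so that the one-week clock starts only when QTcF is at or below 500 ms and no more than 60 ms above baseline. This matches the existing rule for ending hourly ECGs, and the QTcF restart condition can then no longer be met while the interruption rule still is.

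The cost is a one-word amendment. It adds no threshold, visit or procedure. Some interruptions will last longer, but only while the subject is at a QTcF for which the section already requires the drug to be held.

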5.4.1.2.17 Endocrine Disorders

Treatment-emergent elevation of thyroid-stimulating hormone (TSH) has been observed with cabozantinib treatment. Currently available data are insufficient to determine the mechanism of thyroid function test alterations and its clinical relevance. Routine monitoring of thyroid function and assessments for signs and symptoms associated with thyroid dysfunction is recommended before initiation and during treatment with cabozantinib. Management of thyroid dysfunction (e.g., symptomatic hypothyroidism) should follow accepted clinical practice guidelines.

5.4.1.2.18 Musculoskeletal and Connective Tissue Disorders

Cabozantinib appears to represent minimal risk of adverse musculoskeletal effects based on nonclinical GLP-compliant toxicology studies. The development of new or progressive, unexplained musculoskeletal symptoms such as pain or weakness should be assessed for underlying causes.

Rhabdomyolysis has been reported. Cabozantinib should be discontinued in subjects with serious and life-threatening rhabdomyolysis and interrupted if less severe forms occur when there are no other clear causes. Reinitiation of cabozantinib treatment must be discussed with and approved by the Principal Investigator. Therapy of rhabdomyolysis should include supportive care and standard medical intervention.

5.4.1.2.19 Respiratory, Thoracic and Mediastinal Disorders

Dyspnea has been reported in clinical studies with cabozantinib. Symptoms should be managed according to locally accepted clinical practice including an assessment for underlying causes. Pulmonary embolism should be considered as possible cause of new onset dyspnea given the risk of thrombosis associated with inhibition of VEGF signaling. Furthermore, fistula formation and pneumonia have been reported in subjects treated with cabozantinib and should be considered as clinically indicated in subjects presenting with pulmonary symptoms.

5.4.1.2.20 Electrolyte Abnormalities

Electrolyte abnormalities, including hypocalcemia, hypokalemia, hypomagnesemia, and hypophosphatemia have been noted in subjects treated with cabozantinib. In some cases these have been Grade 3 or 4 and/or serious. These laboratory values should be evaluated routinely. Deficits should be corrected when an electrolyte abnormality is noted in order to avoid worsening. Correction of electrolyte abnormalities should be accompanied by increased frequency of monitoring.

5.4.2 Management of AEs Associated with Nivolumab and Ipililumab

The assigned dose for Nivolumab 3 mg/kg IV every 3 weeks followed by 480mg every 4 weeks.

The assigned dose for Ipilimumab 1 mg/kg for a maximum of up to 4 doses.

Dose reductions are not allowed for the IO agents. AEs associated with the IO agents are managed with dose delays.

For more detailed guidance on management of non-hepatocellular AEs associated with IO agents please see Appendix A. For recommendations on management of hepatocellular toxicity and dose modifications of both cabozantinib and IO agents, see Section 5.4.3.

5.4.2.1 Dose Delay Criteria for the Nivolumab and Ipililumab

Administration of the Nivolumab and Ipililumab should be delayed, for any of the following:

- Any Grade 2 non-skin, drug-related AE, with the exception of fatigue
- Grade 2 drug-related creatinine, AST, ALT, and/or total bilirubin abnormalities
- Any Grade 3 skin, drug-related AE
- Any Grade 3 drug-related laboratory abnormality, with the following exceptions:
 - Grade 3 lymphopenia does not require dose delay
 - Grade 3 amylase or lipase abnormalities that are not associated with symptoms or clinical manifestations of pancreatitis do not require a dose delay.
 - Grade 3 AST, ALT or total bilirubin may require dose discontinuation. (See Section 5.4.3)
- Grade 4 amylase or lipase value necessitates dose delay for the anti-PD-(L)1 and anti-CTLA-4 and
 abdominal imaging to rule out pancreatitis regardless of presence or absence of symptoms. If the
 diagnostic radiology scan shows no evidence of pancreatitis, the anti-PD-(L)1 and anti-CTLA-4 may
 CONFIDENTIAL Cabozantinib + Nivolimab + Ipililumab Protocol Required Elements

be resumed once the amylase and lipase values return to Grade 3 or lower as long as the subject remains asymptomatic.

 Any AE, laboratory abnormality, or intercurrent illness which, in the judgment of the Investigator, warrants delaying the dose of study medication.

Immuno-oncology agents are associated with AEs that differ in severity and duration from AEs caused by other therapeutic classes. Early recognition and management of AEs associated with immuno-oncology agents may mitigate severe toxicity. Management algorithms or tables (Section 5.4.3 and Appendix A) have been developed to assist investigators in assessing and managing the following groups of AEs:

- Gastrointestinal
- Renal
- Pulmonary
- Hepatic
- Endocrinopathy
- Skin
- Neurological
- Myocarditis
- Infusion-related Reactions

5.4.2.2 Criteria to Resume Nivolumab and Ipililumab

Delayed doses of Nivolumab and Ipililumab should be administered as soon as the subject meets criteria to resume treatment. If a dose has been delayed, the subject should not wait until the next scheduled dosing date.

Subjects may resume treatment with these study drugs when the drug-related AE(s) resolve to Grade \leq 1 or baseline value, with the following exceptions:

- Subjects may resume treatment in the presence of Grade 2 fatigue.
- Subjects who have not experienced a Grade 3 drug-related skin AE may resume treatment in the presence of Grade 2 skin toxicity.
- Systemic corticosteroids for control of infusion reactions or irAEs must have been tapered to a dose level ≤ 10 mg/day of prednisone equivalent before resuming treatment with Nivolumab and Ipililumab.

- For subjects with AST, ALT, and/or total bilirubin abnormalities, dosing may resume when laboratory values return to baseline grade and corticosteroid therapy has been tapered to no higher than the equivalent of 10 mg of prednisone per day.
 - Note: Drug-related ALT or AST > 3x ULN in combination with total bilirubin > 2x ULN without reasonable other explanation, consistent with DILI mandates permanent discontinuation of all study drugs.

Note: Nivolumab and Ipililumab, or Ipililumab alone, may be continued after a Grade 3 ALT or AST has been observed and managed appropriately after a positive benefit risk ratio has been determined and the Principal Investigator has been consulted (See Section 5.4.3)

- Drug-related pulmonary toxicity, diarrhea, or colitis must have resolved to baseline before
 treatment is resumed. Subjects with persistent Grade 1 pneumonitis after completion of a steroid
 taper over at least 1 month may be eligible for retreatment if discussed with and approved by the
 Principal Investigator.
- Drug-related endocrinopathies adequately controlled with only physiologic hormone replacement may resume treatment.
- If all study treatment is interrupted for > 12 weeks, the subject must be permanently discontinued from study treatment unless approved by the Principal Investigator.

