5.4.2.3 Criteria for Discontinuation of Nivolumab and Ipililumab

Criteria for discontinuation of both Nivolumab and Ipililumab during the combination therapy period or the Nivolumab alone after no additional Ipililumab is to be given are specified in this section. If a subject meets criteria for discontinuation and the Investigator is unable to determine whether the event is related to both or one study drug, the subject should discontinue both Nivolumab and Ipililumab with the exception of certain cases of liver function test elevation (See Section 5.4.3).

Nivolumab and Ipililumab should both permanently discontinued for any of the following reasons:

- Any Grade 2 drug-related uveitis, eye pain or blurred vision that does not respond to topical therapy and does not improve to Grade 1 severity within the re-treatment period OR requires systemic treatment;
- Grade 3 drug-related uveitis, pneumonitis, bronchospasm, neurologic toxicity, myocarditis, hypersensitivity reaction, or infusion reaction of any duration;
- Any Grade 3 adrenal insufficiency regardless of control with hormone replacement.
- Any Grade 3 drug-related non-skin AE lasting > 7 days or recurs;
- Grade 3 diarrhea or Grade 3 colitis

- Note: Nivolumab alone can be continued if grade 3 colitis or diarrhea lasts ≤ 7 days or if, upon permanent discontinuation of ipililumab, the Principal Investigator approves continued use due to a possible favorable benefit/risk ratio.
- Grade 3 drug-related thrombocytopenia > 7 days or associated with bleeding;
- Grade ≥ 3 drug-related AST**, ALT**, or total bilirubin;
 - ** In most cases of Grade 3 AST or ALT elevation, Nivolumab and Ipililumab will be permanently discontinued. Nivolimab alone or Nivolumab and Ipililumab may be continued with approval from the Principal Investigator if there is a possible favorable benefit/risk ratio.
- Drug-related ALT or AST > 3x ULN in combination with total bilirubin > 2x ULN without reasonable other explanation, indicative of potential DILI, mandates permanent discontinuation of all study drugs;
- Grade 4 drug-related AE or laboratory abnormality (including but not limited to creatinine, AST, ALT, or total bilirubin);
- Any grade meningoencephalitis, myasthenia gravis, or Guillain-Barré syndrome
- Any event that leads to delay in dosing lasting > 12 weeks from the previous dose.

The following scenarios do not require discontinuation of the ipililumab and/or nivolumab:

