The table below provides suggested guidance on management of hepatotoxicity related to cabozantinib, Nivolumab and Ipililumab.

In the event cabozantinib is interrupted and Nivolumab and Ipililumab delayed due to a Grade 2 abnormality in a serum transaminase (ALT and/or AST) or serum bilirubin, Nivolumab and (if fewer than 4 ipilulumab doses have been administered and no AE has occurred that led to discontinuation of the ipililumab alone) the ipililumab should be resumed upon return of liver function tests to baseline grade, at which time cabozantinib should be resumed with a dose reduction (from either 40 mg qd to 20 mg qd, or 20 mg qd to 20 mg qod as appropriate).

If no additional ipililimab is to be administered, the dose of cabozantinib may be re escalated no sooner than 10 days after re-initiation of cabozantinib. And then can be further escalated no sooner than 14 days thereafter.

Consult with the Principal Investigator to discuss further management should re-challenge be followed by any recurrence of a Grade 2 or higher liver function test.

Dose delays should not alter the timing of other study assessments, including but not limited to tumor imaging.

For additional information on dose modifications of Nivolumab and Ipililumab, refer to Section 5.4.2 or Appendix A.

Suggested Management of Hepatotoxicity Associated with Study Treatment

Severity of LFT ^a Elevations	Dose Modification Guidance	Management/Follow-up Guidance
AST or ALT $> 1 - \le 3x$ ULN and/or total bili $> 1 - \le 1.5x$ ULN	Cabozantinib: Continue cabozantinib per protocol Nivolimab/Ipilulimab: Continue therapy per protocol	Monitor LFTs per protocol. Discontinue concomitant hepatotoxic medications, if possible.

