AST or ALT > 3 - ≤ 5 x ULN or total bili > 1.5 - ≤ 3x ULN	 Cabozantinib: Interrupt cabozantinib dosing. If LFTs return to baseline grade, resume cabozantinib at a reduced dose. After completion of ipililumab, re-escalate cabozantinib dose as per protocol. If no additional ipililumab doses are to be administered, the dose of cabozantinib may be re-escalated no sooner than 10 days after re-initiation of cabozantinib. See above section for additional guidance. Nivolimab/Ipilulimab: Delay therapy per protocol. If LFTs return to baseline grade, resume therapy per protocol. 	 Monitor LFTs twice weekly or more frequently as deemed clinically necessary. If tapering off steroid therapy, monitor LFTs once weekly or more often per clinical judgment^b. If LFTs return to baseline grade, resume with routine monitoring. If LFT elevations persist > 3 days or worsen: Administer 0.5-1 mg/kg/day methylprednisolone or oral equivalent. When LFTs return to baseline grade or CTCAE Grade ≤1, taper steroids over at least 1 month^b. Consider prophylactic antibiotics for opportunistic infections.
AST or ALT > 5x ULN or total bili > 3x ULN or as otherwise specified	 Cabozantinib: Discontinue cabozantinib if ALT or AST > 8x ULN. Otherwise interrupt cabozantinib dosing and resume at a reduced dose after LFTs return to baseline grade (Sponsor approval required) Nivolimab/Ipilulimab: Discontinue therapy for Grade 3 ALT/AST, unless the Investigator in consultation with the Principal Investigator determines a favorable risk/benefit ratio that warrants continuation of both Nivolumab and Ipililumab or of Nivolumab alone 	 Monitor LFTs twice weekly or more frequently as deemed clinically necessary. During steroid taper, monitor LFTs once weekly or more often per clinical judgment^b. For Grade 3: Administer 1.0-2.0 mg/kg/day methylprednisolone IV or IV equivalent. For Grade 4: Administer 2.0 mg/kg/day methylprednisolone IV or IV equivalent. Add prophylactic antibiotics for opportunistic infections. Consult Gastroenterologist. When LFTs return to baseline grade or Grade 2, taper steroids over at least 1 month^b.

		 If LFT elevations do not improve in > 3 days, worsen or rebound: Add mycophenolate mofetil 1g BID. If no response within an additional 3-5 days, consider other immune-suppressants per local guidelines.

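### The note in 5.4.2.2 names ipilimumab as the single agent that may continue after Grade 3 ALT/AST, whereas 5.4.2.3 and the 5.4.3 table name nivolumab

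*Combined protocol and SAP*

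**What the plan says.** Three statements in the combined protocol and SAP set out what may happen to the immunotherapy agents after a Grade 3 ALT or AST elevation.

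- **5.4.2.2, note under the liver bullet:** "Nivolumab and Ipililumab, or Ipililumab alone, may be continued after a Grade 3 ALT or AST has been observed and managed appropriately". A positive benefit-risk judgement and consultation of the Principal Investigator are required, and the note refers the reader to 5.4.3.
- **5.4.2.3, double-asterisk text under the AST/ALT/bilirubin criterion:** the default is "In most cases of Grade 3 AST or ALT elevation, Nivolumab and Ipililumab will be permanently discontinued". The exception is "Nivolimab alone or Nivolumab and Ipililumab may be continued with approval from the Principal Investigator if there is a possible favorable benefit/risk ratio".
- **5.4.3, hepatotoxicity table, row for AST or ALT above 5 times ULN:** the default is again to stop immunotherapy at Grade 3. The wording of the exception is "consultation with the Principal Investigator determines a favorable risk/benefit ratio that warrants continuation of both Nivolumab and Ipililumab or of Nivolumab alone".

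The introduction to 5.4.2 also sends liver toxicity to 5.4.3: "For recommendations on management of hepatocellular toxicity and dose modifications of both cabozantinib and IO agents, see Section 5.4.3".

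**The concern.** The single-agent option in 5.4.2.2 is the reverse of the one in the other two places, including the section that the note cites. This is an operative re-dosing rule after severe liver toxicity. Taken literally, the note permits ipilimumab to go on without nivolumab and leaves out the single-agent option that 5.4.2.3 and 5.4.3 offer. A site that gave ipilimumab alone would comply with 5.4.2.2 and depart from 5.4.2.3. No clause says which section prevails, so a monitor checking adherence to the treatment plan would have no clear basis for calling it a deviation.

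**Working it through.** No arithmetic applies beyond a count, so the texts are compared directly.

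**Step 1. Options allowed after Grade 3 ALT/AST.**

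| Place | Both agents | Nivolumab alone | Ipilimumab alone | Principal Investigator's role |
|---|---|---|---|---|
| 5.4.2.2 note | yes | not named | yes | consulted |
| 5.4.2.3 exception | yes | yes | not named | approval |
| 5.4.3 table | yes | yes | not named | consultation |

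Continuing both agents is the only option common to all three. For the single-agent option, two statements name nivolumab and one names ipilimumab.

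**Step 2. Which text is likely to be wrong.** The Study Design section gives ipilimumab with nivolumab for 4 cycles, then nivolumab without ipilimumab. Section 5.4.2 caps ipilimumab at 4 doses. The scope sentence of 5.4.2.3 provides for discontinuation of both agents "during the combination therapy period or the Nivolumab alone after no additional Ipililumab is to be given". The regimen thus has a combination period and a nivolumab-alone period, and no ipilimumab-only phase. Nor does any section set out ipilimumab dosing without nivolumab. This points to the 5.4.2.2 note as the slip.

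**Step 3. Context that agrees but is not counted.** The Grade 3 colitis/diarrhea rule in 5.4.2.3 keeps nivolumab: "Nivolumab alone can be continued if grade 3 colitis or diarrhea lasts" no more than 7 days. The 5.4.3 text on resuming after a Grade 2 liver abnormality makes only ipilimumab conditional, on fewer than 4 doses having been given and on the requirement that "no AE has occurred that led to discontinuation of the ipililumab alone". The first concerns a different toxicity. The second normally resumes both drugs. Neither decides the Grade 3 liver question, so the count stays at 2 to 1.

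**Step 4. Reach.** The wrong option can matter only when all of the following hold:

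- a patient has Grade 3 ALT/AST;
- the default discontinuation is overridden;
- one agent continues rather than both;
- fewer than 4 ipilimumab doses have been given;
- liver values have returned to baseline grade and steroids are at or below 10 mg/day prednisone equivalent (the liver bullet in 5.4.2.2, to which the note belongs);
- the case is not one of potential drug-induced liver injury, which stops all study drugs;
- the Principal Investigator has been involved.

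The documents give neither a Grade 3 ALT/AST rate nor an override rate, so no number of patients can be attached.

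**The case against.** The best case against raising this is that little turns on it. All three texts let both agents continue, so ipilimumab after Grade 3 ALT/AST is already allowed everywhere, and nothing in the documents shows ipilimumab alone to be harder on the liver than the combination. Recovery to baseline grade, the steroid taper and the Principal Investigator's involvement all come first. This stands, and it limits the size of the point. It does not remove the inconsistency.

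A second objection is that ipilimumab alone might be intended. Eligible patients have already progressed on anti-PD-1/PD-L1 therapy, and 5.4.2.3 recognises that an event may relate to one drug rather than both. This also stands in part: the slip is an inference, so the intent should be confirmed before the text is changed. However, if ipilimumab alone were intended, 5.4.2.3 and 5.4.3 would be the texts needing correction.

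A reader might also infer that 5.4.2.3 and 5.4.3 expressly forbid ipilimumab alone. Neither uses exclusive wording, and 5.4.3 introduces its table as suggested guidance. The firmer conflict is with 5.4.2.3, where a named exception sits under a rule of permanent discontinuation. The table supports that reading.

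Finally, a reader might see the note's use of consultation, against approval in 5.4.2.3, as a further fault in the note. The 5.4.3 table also asks for consultation, so on that matter 5.4.2.3 is the one that differs.

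**Conclusion.** The inconsistency is real and sits in current operative text. After Grade 3 ALT/AST, the 5.4.2.2 note names the opposite single agent from 5.4.2.3 and the 5.4.3 table. That much needs no assumption. That it is a drug-name slip is probable, resting on the 2-to-1 count and the absence of an ipilimumab-only phase. It is worth fixing because it governs re-dosing after severe liver toxicity, although its reach is small.

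Two stronger conclusions might be drawn and are not supported. The note does not direct ipilimumab re-treatment, and it does not expose patients to a drug that the other sections withhold. It is permissive, and those sections already allow ipilimumab within the combination. Nor does the point bear on progression-free survival, the Grade 3 or higher adverse event incidence, the sample size or the analysis.

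**What to change.** In the 5.4.2.2 note, change the single agent that may continue from ipilimumab to nivolumab, after the sponsor's clinicians confirm that this is the intent. Leave the option to continue both agents as it is.

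Do not change only the note from consultation to approval, because that would make it differ from the section it cites. If the Principal Investigator's role is to be made uniform, settle it once and use the same requirement in 5.4.2.2, 5.4.2.3 and 5.4.3.

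The cost is one drug name in a protocol clarification, the review by the two supporting companies and the IRB that section 11 requires for modifications, and a notice to the single site. It is best done before the possible expansion by 1-2 sites, so that new investigators do not start from the inconsistent text.
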